6.1. General Considerations

Statistical analysis of this study will be the responsibility of Eli Lilly and Company. The interpretation of the study results will be the responsibility of the investigator with the Lilly CRP or CRS, pharmacokineticist, and statistician. The CRP or CRS and statistician will also be responsible for the appropriate conduct of an internal review for both the final study report and any study-related material to be authorized by Lilly for publication.

Sponsor standard tables, figures, and listings (TFLs) and supporting programs and software (eg, TAFFY, BEACH, Spotfire) will be utilized for all analyses where a suitable standard exists. Data derivations in this SAP are defined, based upon current Sponsor reporting standards at the time of writing, and may be updated at the time of analysis in order to maintain accordance with the most current Sponsor standards at that time.

In general, continuous variables will be presented using the mean, standard deviation, coefficient of variation, median, minimum, maximum, and number of patients with an observation (n). For categorical variables, the population size (N), the number of patients with events (n), and the percentage of patients with events are usually reported.

All confidence intervals (CIs) will be given at a 2-sided 95%, unless otherwise stated.

The data handling conventions will be used in the analysis are outlined in [Table JZFA.6.1](#).

Table JZFA.6.1. Data Handling Conventions

Term	Definition or Rule
Relative Study Day	If assessment is on or after date of first dose then (date of assessment) – (date of first study drug dose) +1
	If assessment precedes first dose of drug then (date of assessment) – (date of first study drug dose)
	There is no Study Day 0. Study Day 1 is the date of first dose and Study Day -1 is the day before the first dose.
Cycle Day	If assessment is on or after date of first dose in cycle then (date of assessment) – (date of first study drug dose in cycle) +1
	There is no Cycle Day 0. Cycle Day 1 is the date of first dose in that cycle.
Baseline	For change from baseline analyses, baseline value is defined as the last reported measure on or before the first dose date (prior to the dose administration) unless, otherwise, specified.
Entered	Patients who have signed the informed consent form.
Enrolled	Patients who have been assigned to study treatment and received at least 1 dose of any study drug. Enrolled population is the same as the safety population.
Screen Failures	Patients who have signed informed consent, do not meet eligibility criteria and are not enrolled.

Any change to the data analysis methods described in the protocol/SAP will require an amendment ONLY if it changes a principal feature of the protocol/SAP. Any other change to the

data analysis methods described in the protocol/SAP and the justification for making the change will be described in the clinical study report (CSR). Additional exploratory analyses will be conducted as deemed appropriate.

6.2. Handling of Dropouts or Missing Data

Missing data, except dates, will not be imputed. Historical data such as historical diagnosis, historical illness, preexisting conditions and prior therapies should be collected in a sufficiently informative way. For example, in order to be considered as historical illness, events occurring in the same year as study entry should have at least a known month and year for the end date, while events occurring in previous years should have at least a known year for the end date. The start dates and end dates for adverse events and concomitant medications will be imputed following the most recent Sponsors' standards. Partial dates should be reported in all listings and not the imputed date.

6.3. Patient Disposition

A detailed summary of patient disposition will be provided. It will include a summary of the number and percentage of patients entered into the study, and treated as well as number and percentage of patients completing the study (patients who receive 1 cycle of study dose or are evaluable for DLT for Phase 1a and patients who have at least 1 postbaseline tumor assessment for Phase 1b), or discontinuing (overall and by reason for discontinuation of LY3405105). Reason for discontinuation from both the study treatment and the study will be summarized by pre-determined categories.

A listing of primary reasons for study treatment and study discontinuation will also be provided.

6.4. Patient Characteristics

Patient demographics (including age, sex, screening height, weight, body mass index, race, ethnicity, and country) will be reported using descriptive statistics. The summary will include the number of patients for each treatment group and the total across treatment groups.

The following baseline disease characteristics will be summarized by treatment arm: Eastern Cooperative Oncology Group (ECOG) performance status, initial pathological diagnosis, and basis of initial pathological diagnosis.

Patient preexisting condition, historical illness, prior anti-cancer therapies, and other baseline characteristics such as biomarker and genetic alterations at baseline will be summarized as deemed appropriate.

6.5. Treatment Compliance

Study treatment compliance will be assessed as the proportion of dose that is actually taken, relative to what is expected, after accounting for protocol-defined dose adjustments. The actual dose taken will be derived from the difference between the total number of tablets/capsules dispensed and returned over the course of the patient's treatment.

6.6. Concomitant Therapy

All medications will be coded to the generic preferred name according to the current World Health Organization (WHO) drug dictionary. All concomitant medications will be summarized for the safety population using the preferred name.

6.7. Efficacy Analyses

Tumor response data will be tabulated, and further exploratory analyses will be conducted as warranted, grouping patients by tumor type, for the safety population.

6.7.1. Efficacy Definitions

The following definitions for efficacy endpoints will be used:

Overall response rate (ORR) is the proportion of patients who achieved a complete response (CR) or partial response (PR) out of all patients treated. Tumor responses will be measured and recorded using the appropriate guidelines (Response Evaluation Criteria in Solid Tumors [RECIST 1.1; Eisenhauer et al. 2009]). To confirm objective responses, all lesions should be radiologically assessed, and the same radiologic method used for the initial response determination should be repeated at least 4 weeks following the initial observation of an objective response, using the same method that was used at baseline.

Disease control rate (DCR) is defined as the proportion of patients who achieved a best overall response (BOR) of confirmed CR, confirmed PR or stable disease (SD) out of all patients treated. Best response is determined from a sequence of responses assessed. Two objective status determinations of CR before progression are required for a best response of CR. Two determinations of PR or better before progression, but not qualifying for a CR, are required for a best response of PR. A minimum timeframe of 6 weeks is required for a BOR of SD.

Duration of Response (DoR) will be calculated only for responders. It is measured from the date of first evidence of a confirmed response to the date of first progression of disease or the date of death due to any cause, whichever is earlier. For patients who are not known to have died or to have had a progression of disease as of the data-inclusion cut-off date, DoR will be censored at the date of last objective response assessment prior to the date of any subsequent systemic anticancer therapy.

Progression-free survival (PFS) is defined as the time from the date of start of treatment to the first date of radiologically documented PD or the date of death due to any cause, whichever occurs first. For patients who are not known to have died or progressed as of the data-inclusion cut-off date, PFS time will be censored at the date of the last objective progression-free disease assessment prior to the date of any subsequent systemic anticancer therapy.

Time to Response (TTR) is defined as the time from the date of start of treatment to the date measurement criteria for confirmed CR or PR (whichever is first recorded) are first met. For patients who are not known to have achieved CR or PR as of the data-inclusion cut-off date, TTR will be censored at the date of the last objective disease assessment prior to the date of any subsequent systematic anticancer therapy.

Overall survival (OS) is defined as the time from the date of start of treatment to the date of death due to any cause. For patients who are alive, lost to follow-up, or withdrawn from the study at the time of analysis, OS will be censored at the last date the patient is known to be alive.

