10.3.1. Efficacy Analyses

Tumor response data will be tabulated, and further exploratory analyses will be conducted as warranted, grouping patients by tumor type, for the safety population.

Overall response rate (ORR) is the proportion of patients who achieved a CR or PR out of all patients treated. Tumor responses will be measured and recorded using the appropriate guidelines (RECIST v1.1 [Eisenhauer et al. 2009]). To confirm objective responses, all lesions should be radiologically assessed, and the same radiologic method used for the initial response determination should be repeated at least 4 weeks following the initial observation of an objective response, using the same method that was used at baseline.

Disease control rate (DCR) is defined as the proportion of patients who achieved a CR or PR or stable disease (SD) out of all patients treated.

Duration of response (DoR) will be calculated only for responders. It is measured from the date of first evidence of a confirmed response to the date of first progression of disease or the date of death due to any cause, whichever is earlier. For patients who are not known to have died or to have had a progression of disease as of the data-inclusion cutoff date, DoR will be censored at the date of last objective response assessment prior to the date of any subsequent systemic anticancer therapy.

Progression-free survival (PFS) is defined as the time from the date of start of treatment to the first date of radiologically documented progressive disease or the date of death due to any cause, whichever occurs first. For patients who are not known to have died or progressed as of the data-inclusion cutoff date, PFS time will be censored at the date of the last objective progression-free disease assessment prior to the date of any subsequent systemic anticancer therapy.

Time to response (TTR) is defined as the time from the date of start of treatment to the date measurement criteria for confirmed CR or PR (whichever is first recorded) are first met. For patients who are not known to have achieved CR or PR as of the data-inclusion cutoff date, TTR will be censored at the date of the last objective disease assessment prior the date of any subsequent systematic anticancer therapy.

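### PFS and DoR are cut back to before new anticancer therapy only when no event is seen by the cut-off, so later events count but later event-free time does not

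*SAP*

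**What the plan says.** SAP 6.7.1 ends PFS at the "first date of radiologically documented PD or the date of death due to any cause, whichever occurs first". Events after a change of therapy are not excluded. New therapy enters only through the next sentence, which opens "For patients who are not known to have died or progressed as of the data-inclusion cut-off date, PFS time will be censored" and gives the date: such patients are "censored at the date of the last objective progression-free disease assessment prior to the date of any subsequent systemic anticancer therapy".

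DoR is built the same way. It runs "to the date of first progression of disease or the date of death due to any cause, whichever is earlier". Its censoring sentence is limited by "For patients who are not known to have died or to have had a progression of disease as of the data-inclusion cut-off date", and for those patients "DoR will be censored at the date of last objective response assessment prior to the date of any subsequent systemic anticancer therapy".

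Protocol 10.3.1 repeats the structure: "For patients who are not known to have died or progressed as of the data-inclusion cutoff date, PFS time will be censored", with the same cut-back to before new therapy.

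SAP 6.7.2 summarizes the time-to-event endpoints by Kaplan-Meier, descriptively and for Phase 1b only. The Phase 1b schedule (Protocol Table JZFA.2.2) continues imaging until progression, death or study completion, and checks survival every 3 months after treatment. Starting new therapy does not stop either. Neither document has a separate rule for events after new therapy, or a sensitivity analysis on this point.

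**The concern.** Take two patients who stop study drug without progression and start another systemic therapy at month 3. One progresses at month 10 and is an event at month 10. The other is still event-free at the cut-off and is censored back at the last scan before month 3. Whether the months after new therapy count is decided by what happens in those months. Kaplan-Meier needs censoring that carries no information about the later outcome, and this rule breaks that by construction.

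Two coherent conventions exist: count all events and follow everyone through new therapy, or censor everyone at new therapy whatever happens later. The text is a mixture of the two. At stake are the PFS and DoR curves for the five Phase 1b cohorts, and reproducibility: a programmer could reasonably implement any of three rules.

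**Working it through.** The documents give no PFS or DoR figure, so there is none to reproduce. Three rules are compared:

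- **A**: all events count, and event-free patients are followed to their last assessment.
- **B**: as written.
- **C**: every patient who starts new therapy before an event is censored before it.

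**1. Direction against A.** The Kaplan-Meier estimate is S(t) = product over event times up to t of (1 - d/n), with d events among n at risk. A and B have the same events at the same times, so every d is equal. B takes some event-free patients out earlier, so every n under B is at most n under A. Each factor is therefore no larger, and B lies at or below A at every time in any data set.

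**2. Hand example (invented data, 20 patients).**
- Ten have events without new therapy, at months 1, 1.5, 2.5, 3, 3.5, 4, 5, 6, 8 and 10.
- Four are event-free to month 14.
- Six start new therapy at about month 2. Two of them progress, at months 7 and 9, and four stay event-free.

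All rules give 18/20 = 0.90 after the first two events. At month 12:
- A: 12 events among 20, so 8/20 = 40.0%. Median 8 months.
- B: four patients leave at month 2, so 14 remain at risk and 10 more events follow. 0.90 × 4/14 = 25.7%. Median 7 months.
- C: six leave at month 2, so 12 remain and 8 more events follow. 0.90 × 4/12 = 30.0%. Median 6 months.

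B is below A throughout, as step 1 requires. It is below C at month 12 but has the later median, so its position relative to C is not fixed.

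**3. Size.** These inputs are assumptions, not from the documents: exponential PFS with a 5-month median; 10% or 30% of patients starting new therapy before an event, independently of prognosis; the same hazard afterwards; censoring at the start of new therapy; 400,000 simulated patients per setting. Follow-up is uniform over 12-24 months (12-month accrual, cut-off 12 months after the last patient) or 4-16 months (cut-off 4 months after). Protocol 10.3 sets the primary analysis at no more than 1 year after last enrolment, which is an upper limit, so both are possible. True 12-month PFS is 2^(-12/5) = 2^(-2.4) = 19%.

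| New therapy before event | Follow-up (months) | Median, A / B / C | 12-month PFS, A / B / C |
|---|---|---|---|
| 10% | 12-24 | 5.0 / 4.98 / 5.0 | 19% / 18% / 19% |
| 10% | 4-16 | 5.0 / 4.9 / 5.0 | 19% / 17% / 19% |
| 30% | 12-24 | 5.0 / 4.9 / 5.0 | 19% / 16% / 19% |
| 30% | 4-16 | 5.0 / 4.7 / 5.0 | 19% / 13% / 19% |

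With a 12-month true median and 30% new therapy, B reports 10.8 months (4-16 months of follow-up) or 11.1 (12-24).

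**4. If new therapy changes the hazard.** With 30% new therapy, 12-24 months of follow-up and a halved hazard afterwards, the medians are 5.4 (A), 5.1 (B) and 5.0 (C). The written rule is still below A but above C.

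**5. Scale.** Protocol 10.1 plans about 20 patients in each of Cohorts 1-4 and about 30 in Cohort 5. Simulated with a 6-month median and 20% new therapy, the sampling SD of 12-month PFS is about 10 percentage points at n = 20 and 8 at n = 30.

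**The case against.** The strongest reply is that little turns on this. Treatment runs to progression by design, so switching before progression is confined to exits such as toxicity, patient request or investigator decision. The 30% rate is an assumption; at 10% the median hardly moves. The endpoints are secondary and descriptive, no decision rule uses them, and SAP 6.7.2 also lists them patient by patient. All of that stands.

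A reader might infer that the curves are too low by any standard. The documents do not support that: step 4 shows the written rule above the censor-everyone median when new therapy slows events. If new therapy instead doubles the hazard (same setting), 12-month PFS is about 13.5% (A), 12.8% (B) and 18.9% (C). The two coherent rules then differ by 5.4 points, while the written rule is 0.7 from A. The comparator has to be named.

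It can also be said that few later events will be recorded. Protocol 7.7 bars other anticancer therapy while on study and ties progression needing it to discontinuation from the study, which under Protocol 8.2 includes follow-up procedures. If sites work that way, the written rule approaches censoring everyone. But Protocol 5.1.3 and the schedule continue follow-up to death, loss to follow-up or study completion. The documents leave this open, and it does not cure the censoring sentence.

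**Conclusion.** The point holds as a defect in the written rule for PFS and DoR, in both documents. Against the plan's own event definition with full follow-up, the direction is certain: the curve is at or below the full-follow-up curve in any data set. Against censoring everyone at new therapy it is low if the hazard is unchanged, and can be high otherwise.

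Under the assumptions in step 3, the loss in 12-month PFS is about 1 to 6 points (19% reported as 13-18%). The 13% needs both 30% switching and short follow-up, and should not be read as the expected result. The bias is smaller than sampling error in a single cohort, but it runs the same way in all five, and confidence intervals do not reflect it.

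For DoR only the mechanism is established. It covers responders alone, possibly a handful per cohort, and no size can be given. A reader might infer that the Phase 1b efficacy conclusion is at risk. It is not: ORR, the primary endpoint, does not use this rule.

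**What to change.** State one rule for all patients, in the same words, in Protocol 10.3.1 and SAP 6.7.1, for PFS and for DoR. For example:

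*A patient who starts subsequent systemic anticancer therapy before progression or death is censored at the last adequate assessment before that therapy, whether or not an event is recorded later.*

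Show the all-events, full-follow-up analysis as a sensitivity analysis, as far as follow-up after new therapy is captured, and report how many patients per cohort started new therapy before an event. The reverse choice of main and sensitivity analysis would be equally coherent, but it relies more on that follow-up, so Protocol 7.7 and 8.2 would first need reconciling with the schedule. Censoring everyone has its own assumption, that starting new therapy is unrelated to prognosis, which is why both should be shown.

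The cost is one sentence per endpoint in each document and one extra set of curves. The recommended main rule needs no new data. The downside is a few more censored patients.

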6.7.2. Efficacy Analyses

Reported lesion data (target/non-target or measurable/nonmeasurable), investigator assessment of response, all time-to-event endpoints will be listed for all patients. The following efficacy summaries will be provided:

- overall response rate and DCR will be presented with exact 95% CI;
- time to event endpoints, including PFS, DoR, TTR, and OS will be summarized descriptively using the Kaplan-Meier method for Phase 1b only; and
- best percent change in tumor size will be presented using a waterfall plot. All patients with at least 1 pre and postdose target lesion measurement will be shown in the plot.

In Phase 1b dose expansion cohorts, Bayesian models will be used to estimate the posterior probability of activity in terms of ORR (with non-informative prior).

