Table JZFA.2.2. Baseline, On-Study Treatment, and Post Treatment Schedule of Activities for Phase 1b

Procedure	Baseline	All Remaining Parts on Treatment (Cycle = 28 days)					Post Treatment Follow-Up		Instructions
	Days Prior to C1D1	Cycle 1 (± 3 Days)		Cycle 2 (± 3 Days)		Cycle 3-n (± 3 Days)	Short-Term ^a (30 ± 7 Days)	Long-Term (Every 90 ± 7 Days)	
		Day		Day		Day			
		≤ 28	1	15	1	15	1	Visit 801	Visit 802-8XX
Informed consent	X								ICF must be signed before any protocol-specific procedures are performed. Baseline/screening labs or imaging, as part of routine patient care, drawn within the indicated window of C1D1 may be used for both screening/baseline and C1D1 labs.
Physical examination*	X	X	X	X	X	X	X		Perform prior to administration/dispensing of study drug.
Vital signs and weight*	X	X	X	X	X	X	X		Perform prior to administration/dispensing of study drug. Include height (only at baseline), weight, and vital signs (temperature, blood pressure, pulse rate).
Medical history	X								
Inclusion/Exclusion evaluation	X								
Concomitant medication	X	X	X	X	X	X			
AE collection	X	X	X	X	X	X	X	X	CTCAE V4.0. During long-term follow-up, only AEs that are related to study treatment will be followed to resolution.
ECOG performance status or LPS	X	X	X	X	X	X	X		
Radiologic imaging and measurement of palpable or visible lesions	X	X					X	X	Perform according to RECIST v1.1 criterion, by the same method used at baseline, q 8 wk (± 7 days) for the first 6 mo after C1D1 and q 12 wk (± 7 days) thereafter until radiographic disease progression, death, or study completion, whichever occurs first. Perform as scheduled, even if study treatment is delayed or omitted.
ECG	X								Baseline: Predose (single). Perform additional evaluations in the setting of cardiac symptoms and/or at the discretion of the investigator. Perform locally.
Hematology*	X	X	X	X	X	X	X		≤ 3 days prior to start of each cycle, unless more frequent assessment is clinically indicated.

Procedure	Baseline	All Remaining Parts on Treatment (Cycle = 28 days)						Post Treatment Follow-Up		Instructions				
	Days Prior to C1D1	Cycle 1 (± 3 Days)		Cycle 2 (± 3 Days)		Cycle 3-n (± 3 Days)		Short-Term ^a (30 ± 7 Days)	Long-Term (Every 90 ± 7 Days)					
		Day		Day		Day								
		≤28	1	15	1	15	1							
Coagulation	X									Only collected at baseline, unless more frequent assessment is clinically indicated.				

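### Phase 1b time to response is summarised by Kaplan-Meier with progressed and dead non-responders censored, so the curve and any median do not estimate response among treated patients

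*SAP*

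**What the plan says.** SAP 6.7.1 runs TTR from start of treatment to "the date measurement criteria for confirmed CR or PR (whichever is first recorded) are first met". For patients not known to have responded by the cut-off, "TTR will be censored at the date of the last objective disease assessment prior to the date of any subsequent systematic anticancer therapy". Protocol 10.3.1 has the same rule. Neither document handles progression or death separately for TTR.

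SAP 6.7.2 then specifies that "time to event endpoints, including PFS, DoR, TTR, and OS will be summarized descriptively using the Kaplan-Meier method for Phase 1b only". Protocol 10.2 assigns the safety population (everyone who received any study treatment) to all efficacy analyses.

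Three other statements bear on the point:

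- On best response, SAP 6.7.1 says "Two determinations of PR or better before progression, but not qualifying for a CR, are required for a best response of PR", and it requires two CR determinations before progression for a best response of CR.
- On duration, SAP 6.7.1 says "Duration of Response (DoR) will be calculated only for responders". TTR carries no such restriction.
- SAP 6.3 counts as Phase 1b completers "patients who have at least 1 postbaseline tumor assessment for Phase 1b", so it foresees treated patients who have none.

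ORR, the Phase 1b primary endpoint, is a proportion of all treated patients with an exact 95% interval.

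**The concern.** Kaplan-Meier assumes that a censored patient keeps the same future chance of the event as patients still under observation. Under the SAP's own response rule, that chance is zero for a non-responder who has progressed or died. Removing such patients from the risk set hands their share of probability to those who remain, so 1-KM rises above the proportion who respond.

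The TTR sentence does not itself say that all treated patients are included. That reading follows from the safety-population rule, the lack of a responder restriction, and the censoring rule for non-responders, which would have no use in a responder-only summary.

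At stake is a report in which a TTR curve ends above the ORR shown beside it, or a median time to response appears for a cohort in which most patients never responded. In signal-finding cohorts of about 20 or 30 patients, that could overstate activity to a reader.

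**Working it through.** **The plan's own figures.** The documents give no figure for TTR. The nearest efficacy figures are the Clopper-Pearson intervals in Protocol Table JZFA.10.1. All ten reproduce, for example 3/20: 0.03-0.38, 5/20: 0.09-0.49 and 5/30: 0.06-0.35. They concern ORR and are not affected.

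**Direction.** At scan j, among patients still at risk, let r_j be the probability of response and q_j the probability of leaving without response.

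- Cumulative incidence of response = Σ_j r_j Π_{i<j}(1 − r_i − q_i)
- 1-KM = 1 − Π_j(1 − r_j) = Σ_j r_j Π_{i<j}(1 − r_i)

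Since 1 − r_i − q_i ≤ 1 − r_i, 1-KM is never smaller. The two are equal only if nobody leaves before the last response.

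**Inputs for size.** Scans every 8 weeks "for the first 6 mo after C1D1 and q 12 wk" thereafter (Protocol Table JZFA.2.2) give weeks 8, 16, 24, 36 and 48. Cohort sizes are 20 and 30 (Protocol 10.1). True ORR, response timing and time to progression are assumptions.

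**Worked cohort (assumed).** There are 4 responders among 20: 2, 1 and 1 at weeks 8, 16 and 24. Non-responders leave as follows: 6, 4 and 2 at those scans and 4 at week 36. Events precede censorings at ties.

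| Week | At risk | Responses | Factor | 1-KM | Cumulative incidence |
|---|---|---|---|---|---|
| 8 | 20 | 2 | 18/20 | 10.0% | 2/20 = 10% |
| 16 | 20−2−6 = 12 | 1 | 11/12 | 17.5% | 3/20 = 15% |
| 24 | 12−1−4 = 7 | 1 | 6/7 | 29.3% | 4/20 = 20% |

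1 − (18/20)(11/12)(6/7) = 0.293 against an ORR of 0.20. No median is reached.

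**A more extreme cohort (assumed).** Responses occur at weeks 8, 8, 16 and 36; non-responders are censored at weeks 8 (9), 16 (4), 24 (2) and 36 (1). Then 1 − (18/20)(8/9)(1/2) = 0.60, so a median of 36 weeks would be reported although 4/20 = 20% responded.

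**Simulation.** 5,000 trials per setting. Responders respond at weeks 8/16/24 in 60/30/10%. Non-responders have exponential progression times with a median of 24, 12 or 8 weeks, rounded up to the next scan and censored there.

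| n | True ORR | Mean 1-KM (24/12/8 wk) | KM median reached (24/12/8 wk) |
|---|---|---|---|
| 20 | 20% | 22.7 / 25.9 / 30.0% | 0.8 / 4.0 / 10.5% |
| 20 | 30% | 33.3 / 37.9 / 43.4% | 8.2 / 18.8 / 33.7% |
| 30 | 20% | 22.4 / 25.8 / 29.9% | 0.0 / 1.2 / 6.5% |
| 30 | 30% | 33.5 / 37.8 / 43.4% | 4.4 / 13.6 / 29.0% |

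Across these settings 1-KM exceeds the observed ORR, by any amount, in 80-92% of n=20 cohorts and 91-98% of n=30 cohorts. Not every median is spurious: with n=20 and true ORR 30%, the binomial probability of at least 10 responders is 4.8% (0.3% at true ORR 20%).

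**Milder settings.**

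- Earlier responses (80/20/0%), n=20: mean 1-KM is 21.0/22.1/23.7% for ORR 20% and 31.6/33.2/35.2% for ORR 30%. It exceeds the observed ORR in 54-72% of cohorts (70-86% at n=30).
- True ORR 10%, n=20: the mean excess is 1.3-5.4 points (60/30/10) or 0.5-1.9 points (80/20/0), and a median is rarely reached.
- An excess above 5 points at n=20 and ORR 20% occurs in 14/43/64% of cohorts (60/30/10) or 2/12/30% (80/20/0).
- All responses at the first scan and every patient scanned: no excess.

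**Patients without a post-baseline scan.** The documents do not say where they are censored. If it is day 1 (assumption), they leave the TTR risk set but stay in the ORR denominator. With 4 responders at week 8 and 3 of 20 unscanned, 1-KM = 4/17 = 23.5% against 20%. If 15% are unscanned (assumption), first-scan-only responses give about 0.20/0.85 = 23.5% and 0.30/0.85 = 35.3%.

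**The case against.** The strongest reply is that little depends on TTR. It is one of several secondary efficacy endpoints in a non-randomised study whose intervals are for reference, not decisions. The probability of response is reported separately as ORR over all treated patients, and individual TTR values will be listed. The SAP says the summary is descriptive and names neither a median nor a 1-KM display. Kaplan-Meier with progression censored also keeps a narrow meaning, as a summary of the response hazard among patients still under assessment. The size rests on assumed timing: with early responses or a low ORR the excess is small, and at ORR 20% and n=20 the mean excess of about 1-10 points lies well inside the exact interval for 4/20 (0.06-0.44). The day-1 censoring of unscanned patients is not written anywhere.

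Most of this stands, and it limits the importance of the point. It does not remove the error. A median is the usual output of a Kaplan-Meier summary, and readers will take a TTR curve as time to response in the cohort, which it does not estimate. Calling it descriptive does not help if the figure describes no population of interest. The direction of the distortion needs no timing assumption.

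**Conclusion.** The concern holds. Followed as written, the plan treats patients who can no longer respond as if they still could, so its TTR curve is not a valid estimate of response over time in treated patients, and its median is not the median in responders.

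The direction is certain; the size is conditional. For true ORRs of 20-30%, the mean excess over ORR runs from about 1 to 13 points across the two response-timing patterns and the three progression rates simulated. It is smaller at ORR 10% and nil in the first-scan-only case with complete scanning. A Kaplan-Meier median appears in a minority of cohorts.

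The damage is confined to one descriptive secondary summary. ORR, its exact interval, the Bayesian ORR estimate, the sample size and the monitoring rules do not use TTR. It should be corrected before reporting, but it does not threaten the primary result.

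**What to change.** In SAP 6.7.2, remove TTR from the Kaplan-Meier list. In SAP 6.7.1, restrict TTR to confirmed responders and drop its censoring sentence, as the SAP already restricts DoR to responders. Report the number of responders, median and range.

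If a curve over all treated patients is wanted, use the cumulative incidence of confirmed response with progression, death and new anticancer therapy as competing events, and state how patients without a post-baseline scan are handled.

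Until Protocol 10.3.1 is aligned at the next amendment, the two documents will differ on TTR. Protocol 10.3 allows a change that does not alter a principal feature if it is described and justified in the SAP and CSR, so a short justification should accompany the edit. A separate protocol amendment should not be needed. The cost is the SAP wording and one simpler table, with no added data or patient burden.
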